4.6. Patient-Reported Outcomes Analyses

The patient reported outcomes (PROs) will be used to compare changes in cancer-related symptoms, physical function, adverse effect of diarrhea, and other health-related quality of life (HRQoL) outcomes between treatment arms and generate health utility data. The analyses for PROs will be conducted in the ITT population. The following PRO instruments are utilized:

- Worst pain NRS
- EORTC-QLQ-30
- EORTC IL19: Physical Function
- EQ-5D-5L
- PGIS (Patient's Global Impression of Severity)-Cancer Symptoms
- mBPI-SF
- PRO-CTCAE Items for Diarrhea and Injection Site Pain and Swelling

Time to sustained worsening of worst pain (based on the Worst Pain NRS) is defined as the time from randomization to the first increase (≥ 2 points) in the weekly average of the worst pain score with confirmation in the next consecutive week. Participants not known to have sustained worsening will be censored at the last documented assessment. Time to sustained worsening of worst pain will be summarized for each arm by the Kaplan-Meier method and will be compared between the arms using the stratified log-rank test. Additional cutoff values of increase (e.g., ≥ 3 points, ≥ 4 points) may be explored as sensitivity analyses if deemed appropriate. Sensitivity analysis will be done by including death as part of the event definition. Additional sensitivity analyses for time to worsening without confirmation in the next consecutive week may be performed if deemed appropriate. A standard analgesic categorization algorithm such as WHO analgesic ladder will be used to analyze the data, along with the worst pain, as an additional analysis. This will be detailed in the PRO SAP.

Time to worsening of physical function (based on either EORTC-QLQ-30 or EORTC IL19) is defined as the time from randomization to the first \geq 10-point decrease from baseline with confirmation at the next cycle. Participants not known to have worsening will be censored at the last documented assessment. Sensitivity analysis will be done by including death as part of the

event definition. Time to worsening of physical function will be summarized for each arm by the Kaplan-Meier method, and the stratified log-rank test will be used to compare between the 2 arms.

For EORTC-QLQ-30, EORTC IL 19, EQ-5D-5L, mBPI-sf, PGIS, a summary of change from baseline will be provided. For each participant with data from baseline and at least 1 post-baseline visit, change from baseline at each time point, and the maximum change from baseline score will be calculated for each scale of each instrument if appropriate.

PRO-CTCAE items for diarrhea and injection site pain and swelling will be summarized by visit and overall for each treatment arm.

Compliance will be assessed for each instrument. The compliance rate will be calculated at baseline, per week (if appropriate) and per cycle. The number of participants with expected assessments at each post-baseline visit is the number of participants who have received the study drugs in a previous visit. For the Worst Pain NRS, participants will be considered compliant if they have completed \geq 50% of the daily assessments during each period (e.g., week, cycle). A 7-day average score regardless of dosing will be calculated for each consecutive week starting from cycle 1 day 2, if the participant is compliant for the period (completed 4 days out of the 7-day period). A 7-day average score based on any available data may also be calculated as sensitivity analysis even if the compliance rate is lower than 50%. For other instruments, the number of missing and incomplete questionnaires and/or assessments by visit will be summarized for each instrument and treatment arm.

The cycle 1 day 1 (pre-dose) visit will be considered as baseline for all PRO analyses. The analysis for change from baseline will be based on the participants who have baseline and at least 1 post-baseline data.

Further details about PRO analyses will be described in a separate PRO SAP.

4.7. (Other) Safety Analyses

The other safety analyses will be conducted in the safety population.

4.7.1. Extent of Exposure

The number of cycles received, dose omissions, dose reductions, dose delays, and dose intensity will be summarized for all treated patients by treatment arm/study drug as deemed appropriate. The derivations for each study drug are provided below.

Imlunestrant/Exemestane/Abemaciclib

- duration of therapy (weeks) = (date of last dose date of first dose + 1) /7
- cumulative dose (mg) = sum of all doses actually received
- dose intensity (mg/week) = (cumulative dose) ÷ (duration of therapy)
- planned dose intensity (mg/week) = assigned daily dose (mg) * 7
- relative dose intensity (%) = (dose intensity / planned dose intensity)*100

Fulvestrant

- duration of therapy (weeks) = (date of last cycle Day 1 date of first dose + 28) /7, if the last dosing date is in cycle 1, then duration of therapy (weeks)= (date of last dose in cycle 1-date of first dose+14) / 7
 - if the patient died or was lost to follow-up within the date of last dose +length of interval (14 days or 28 days), then duration of therapy = (date of death or date of last contact date of first dose)/7
- cumulative dose (mg) = sum of all doses
- dose intensity (mg/week) = (cumulative dose level) ÷ (duration of therapy)
- planned dose intensity (mg/week) = planned dose per infusion (mg) / 4
- relative dose intensity (%) = (dose intensity / planned dose intensity) * 100

Duration of therapy for patients with certain characteristics may be summarized by treatment arm.

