	Relative Day within a Cycle	≤28	Day 1	Day 15° (± 3)	Day 1 (± 3)	Day 1 (± 3)	Day 30 (± 7)	(± 14)		
Procedure Category	Procedure								Protocol Reference	Instructions
Clinical Tumor Assessment	Tumor measurement (palpable or visible)	Х			See I	nstructions			Section 8.1 and Section 10.3 Appendix 3	 Visible tumor (such as skin lesions) should be documented by photography, and each photographic image of the tumor should include a ruler. If measurable, caliper measurements should be recorded. Images will be collected for central storage for BIRC review Perform at RECIST response assessment intervals outlined below
Tumor Assessment	Radiologic imaging according to RECIST ^b	Х			See I	nstructions			Section 8.1 and Section 10.3 Appendix 3	 Required for all patients Perform according to RECIST v1.1 criteria by the same method used at baseline CT or MRI scan of the chest, abdomen, and pelvis performed with IV contrast when possible^b Response assessments should occur at baseline and then at the following intervals relative to Cycle 1 Day 1: every 8 weeks (±4 days) for the first 12 months and then every 12 weeks (±4 days) thereafter, until radiographic disease progression, death, start of a new anticancer therapy or study completion, whichever occurs first. Perform as scheduled, regardless of any treatment delays or interruptions Perform within 14 days of clinical progression A central radiology vendor will be used to collect and store images for BIRC review

	Study Period	Baseline	Study Treatment (Cycle =28 days)					ontinuation ow-Up		
	Cycle	Screening	1 ar	nd 2	4 and Beyond (if Applicable)		Short-Term Follow-Up ^a	Long-Term Follow-Up ^a		
	Visit	0	1,3	2, 4	5	6 and Beyond (if Applicable)	801	802–8XX		
	Relative Day within a Cycle	≤28	Day 1	Day 15° (± 3)	Day 1 (± 3)	Day 1 (± 3)	Day 30 (± 7)	(± 14)		
Procedure Category	Procedure								Protocol Reference	Instructions

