Participants will be randomized 1:1:1 between 3 treatment arms (Arm A: Arm B: Arm C) and will be treated until disease progression or other discontinuation criteria are met (Section 7.1).See also schema (Section 1.2)

- Arm A: Imlunestrant 400 mg orally QD on Days 1 to 28 of a 28-day cycle
- Arm B: Investigator's Choice Endocrine Therapy
 - Exemestane 25 mg orally QD on Days 1 to 28 of a 28-day cycle **OR**
 - Fulvestrant 500 mg intramuscularly on Days 1 and 15 of Cycle 1, then on Day 1 of Cycle 2 and beyond
- Arm C: Imlunestrant + Abemaciclib
 - o Imlunestrant 400 mg orally QD on Days 1 to 28 of a 28-day cycle
 - o Abemaciclib 150 mg orally BID on Days 1 to 28 of a 28-day cycle

Arm C was added to the study (amendment a) after first patient visit for Arms A and B. Randomization of participants will continue in Arms A and B (1:1) until amendment a is approved and implemented, at which point participants will be randomized 1:1:1 (A:B:C) until the target enrollment for Arms A and B (a total number of approximately 640 participants) is met.

The study will consist of a 28-day *screening phase*; followed by a *treatment phase*; and a *post-treatment phase*, which includes safety, efficacy, and survival follow-up. Investigator's Choice Endocrine Therapy (fulvestrant or exemestane) must be selected prior to randomization.

Participants will be randomized using the following stratification factors:

- previous treatment with any CDK4/6 inhibitor (yes versus no)
- presence of visceral metastases (yes versus no); visceral includes lung, liver, brain, pleural, and peritoneal involvement, and
- region (East Asia versus North America/Western Europe versus Others).

The primary study objectives are to

- compare the PFS of Arm A to Arm B in the ITT population
- compare the PFS of Arm A to Arm B in the *ESR1*-mutation detected population, and
- compare the PFS of Arm C to Arm A in the ITT population.

To control the overall type I error rate, a graphical approach will be applied to test these PFS hypotheses hierarchically. Initially, the overall 1-sided alpha level of 0.025 will be split between PFS for Arm A versus Arm B in the ITT population and PFS for Arm A versus Arm B in the

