6.1. Study Intervention(s) Administered

	Arm A Imlunestrant	Arm B Investigator's Choice Endocrine Therapy		Arm C Imlunestrant + Abemaciclib	
Treatment	Imlunestrant	Fulvestrant	Exemestane	Imlunestrant	Abemaciclib
Dose	400 mg	500 mg	25 mg	400 mg	150 mg
Schedule	QD in 28-day continuous cycles	500 mg on C1D1 and C1D15 and then on Day 1 of a 28-day cycle starting at Cycle 2	QD in 28-day continuous cycles	QD in 28-day continuous cycles	BID in 28-day continuous cycles
Route	Oral	Intramuscular injection of two 250 mg injections	Oral	Oral	Oral
Authorized as defined by EU Clinical Trial Regulation	Not authorized in EU	Authorized and used according to EU authorization	Authorized and used according to EU authorization	Not authorized in EU	Authorized and used according to EU authorization

Abbreviations: BID = twice daily; C = cycle; D = day; QD = once daily.

Imlunestrant will be administered orally, 400 mg QD on Days 1 to 28 on a 28-day cycle. The imlunestrant doses will be administered at approximately the same times on each day. Patients should not consume any food at least 1 hour before and at least 2 hours after administration imlunestrant. Fasting requirements are also described in the patient diary.

The Investigator's Choice of Endocrine Therapy will be limited to fulvestrant or exemestane.

Fulvestrant will be administered 500 mg intramuscularly into the buttocks slowly as two 250 mg injections, one in each buttock on Days 1 and 15 of Cycle 1 of a 28-day cycle, then on Day 1 of Cycle 2 and beyond. However, for patients with moderate hepatic impairment (defined as Child-Pugh Class B), including any patient who develops moderate hepatic impairment during study treatment, fulvestrant 250 mg should be administered intramuscularly into the buttock slowly as one 250-mg injection. See local approved label for additional instructions.

Exemestane will be supplied as 25 mg and administered orally, 25 mg QD. See local approved label for additional instructions.

Abemaciclib will be administered orally, 150 mg BID on Days 1 to 28 on a 28-day cycle. The abemaciclib doses will be administered at approximately the same times on each day (see Section 6.1.4).

Packaging and labeling

Study interventions will be supplied by the sponsor or its designee in accordance with current Good Manufacturing Practice. Study interventions will be labeled as appropriate for country requirements.

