6.1.1. Selection and Timing of Doses

A cycle is defined as an interval of 28 days during treatment period. The 28-day cycle length should be maintained throughout the treatment phase regardless of dose interruptions. Patients will begin dosing assigned treatment on C1D1.

Treatment will continue until progression, unacceptable toxicity, or other discontinuation criteria are met (Section 7.1).

Patients with documented progressive disease (PD) as determined by the investigator may be allowed to continue study treatment if the patient is tolerating study drug and, in the opinion of the investigator, the patient is deriving clinical benefit from continuing study treatment and continuation of treatment is approved by the Sponsor. In addition to the permitted protocol windows (see Schedule of Activities, Section 1.3), a delay for a maximum of 7 days of a cycle start not due to an AE, but due to holiday, weekend, bad weather, or other unforeseen circumstances, will be permitted and not counted as a protocol deviation. Response assessments should remain on the original schedule (see Schedule of Activities, Section 1.3).

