1.2. Study Design

In the protocol amendment (a), participants will be randomized 1:1:1 between 3 treatment arms (Arm A: Arm B: Arm C) and will be treated until disease progression or other discontinuation criteria are met (Protocol Section 7).

- Arm A: Imlunestrant 400 mg orally QD on Days 1 to 28 of a 28-day cycle
- Arm B: Investigator's Choice Endocrine Therapy
 - Exemestane 25 mg orally QD on Days 1 to 28 of a 28-day cycle OR

- Fulvestrant 500 mg intramuscularly on Days 1 and 15 of Cycle 1, then on Day 1 of Cycle 2 and beyond
- Arm C: Imlunestrant + Abemaciclib
 - Imlunestrant 400 mg orally QD on Days 1 to 28 of a 28-day cycle
 - Abemaciclib 150 mg orally BID on Days 1 to 28 of a 28-day cycle

Arm C was added to the study (amendment a) after first patient visit for Arms A and B. All arms will be closed at the same time. Randomization of participants will continue in Arms A and B (1:1) until amendment (a) is approved and implemented, at which point participants will be randomized 1:1:1 (A:B:C) until the target enrollment for arms A and B (a total number of approximately 640 participants) is reached.

Investigator's Choice Endocrine Therapy (fulvestrant or exemestane) must be selected prior to randomization. Participants will be randomized using the following stratification factors:

- previous treatment with any CDK4/6 inhibitor (yes versus no)
- presence of visceral metastases (yes versus no); visceral includes lung, liver, brain, pleural, and peritoneal involvement, and
- region (East Asia versus North America/Western Europe versus Others).

The primary study objectives are to

- compare the PFS of Arm A to Arm B in the ITT population
- compare the PFS of Arm A to Arm B in the ESR1-mutation detected population, and
- compare the PFS of Arm C to Arm A in the ITT population.

The schema of the study is shown below.

Note: *ESR1*-mutation status will be centrally determined in plasma by Guardant 360 ctDNA assay from a blood draw at baseline.

Abbreviations: AI = aromatase inhibitor; CDK = cyclin-dependent kinase; ctDNA = Circulating tumor DNA; ER+ = estrogen receptor positive; FPV = first patient visit; HER2- = human epidermal growth factor receptor 2 negative; mTOR = mammalian target of rapamycin; n = number of participants; PI3K = phosphoinositide 3-kinase; PO = orally; QD = once daily; R = randomization; SERD = selective estrogen receptor degrader.

2. Statistical Hypotheses

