As the overall alpha is initially split between H_1 and H_2 , the study will be considered positive (for Arm A versus Arm B) if either PFS in the ITT population (H₁) or PFS in the *ESR1*-mutation detected population (H₂) is statistically significant. The power and associated sample sizes for H₁ and H₂ are based on the initial allocation of alpha. The analysis population for the first primary hypothesis (PFS for Arm A versus Arm B in the ITT population) is all participants randomized to Arm A and Arm B. The primary analysis of PFS for Arm A versus Arm B in the ITT population will be performed after approximately 480 investigator-assessed events have been observed (that is, a 25% censoring rate) in Arm A and Arm B. Assuming a PFS hazard ratio of 0.74, a total of 480 events yields at least 76% power to detect superiority of imlunestrant Arm A over Arm B with the 1-sided log-rank test at the significance level of 0.005. If H1 can be tested at the full alpha level of 0.025 after recycling per the graphical approach (Figure 4.4), the same number of events can yield at least 91% power with the 1-sided log-rank test. The median PFS of Arm B is assumed to be 4.3 months, and the hazard ratio of 0.74 amounts to an approximate 1.5-month improvement in median PFS under the assumption of exponential survival distribution. The assumed median PFS of Arm B is estimated based on an unpublished metaanalysis of historical controls.

The analysis population for the second primary hypothesis (PFS for Arm A versus Arm B in the *ESR1*-mutation detected population) is the *ESR1*-mutation detected subset in Arm A and Arm B. The primary analysis of PFS will be performed after approximately 192 investigator-assessed events have been observed in the *ESR1*-mutation detected subset. Assuming a PFS hazard ratio of 0.57, a total of 192 events yields approximately 97% power to detect superiority of Arm A over Arm B with the 1-sided log-rank test at the significance level of 0.02. Assuming the median PFS of Arm B in the subset is 3.6 months, the hazard ratio of 0.57 amounts to an approximate 2.7-month improvement in median PFS under the assumption of exponential survival distribution.

The power and sample size for H_3 is based on the 1-sided alpha level of 0.025 assuming that both H_1 and H_2 are rejected. The analysis population of the third primary hypothesis (PFS for Arm C

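### The fulvestrant relative dose intensity in SAP 4.7.1 leaves the Cycle 1 Day 15 injection out of the planned dose, so exact on-schedule dosing for n cycles reads (n+1)/n instead of 100%

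*SAP*

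**What the plan says.** SAP 1.2 gives the schedule as "Fulvestrant 500 mg intramuscularly on Days 1 and 15 of Cycle 1, then on Day 1 of Cycle 2 and beyond", and Protocol 6.1 agrees: "500 mg on C1D1 and C1D15 and then on Day 1 of a 28-day cycle starting at Cycle 2". With 28-day cycles (Protocol 6.1.1), that is n + 1 injections over n cycles.

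For fulvestrant, SAP 4.7.1 then defines:

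- cumulative dose as the total of all doses, so Day 15 of Cycle 1 is included;
- duration of therapy in weeks as (Day 1 of the last cycle minus first dose, plus 28)/7, or, if the last dose falls in Cycle 1, (last dose minus first dose, plus 14)/7;
- a shorter duration, ending at death or last contact, if either falls within the dosing interval after the last dose;
- "planned dose intensity (mg/week) = planned dose per infusion (mg) / 4";
- relative dose intensity as received intensity divided by planned intensity, times 100.

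For the daily oral drugs, planned intensity is the assigned daily dose times 7. No footnote or other section of either document adjusts the fulvestrant planned rate for Day 15.

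**The concern.** The Day 15 injection is in the numerator and not in the denominator. The same section recognises the 14-day Cycle 1 interval when it sets duration, so the omission from the planned rate looks like an oversight.

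A reader takes 100% to mean dosed as planned. Here it does not, and the overstatement is largest in patients who stop early. On-schedule dosing would look like over-dosing, and a missed injection could look like full dosing. The oral drugs read 100% when taken as planned, so the same column would mean different things for different drugs. Fulvestrant also has no other received-to-planned ratio: Protocol 9.4.2.6 assesses compliance only for the three oral drugs, and SAP 4.8.6 treats fulvestrant compliance as assured by administration at the site.

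**Working it through.** The plan states a formula but no value, so there is no figure of its own to reproduce.

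**On-schedule dosing, n cycles.**

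- Received dose: 500(n+1) mg.
- Duration: (28(n−1) + 28)/7 = 4n weeks.
- Planned intensity: 500/4 = 125 mg/week.
- Relative dose intensity: [500(n+1)/(4n)]/125 = (n+1)/n.

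| Cycles n | Received (mg) | Weeks | mg/week | Reading |
|---|---|---|---|---|
| 1 | 1000 | 4 | 250 | 200% |
| 2 | 1500 | 8 | 187.5 | 150% |
| 4 | 2500 | 16 | 156.25 | 125% |
| 5 | 3000 | 20 | 150 | 120% |
| 6 | 3500 | 24 | 145.8 | 116.7% |
| 12 | 6500 | 48 | 135.4 | 108.3% |

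The dose per injection cancels, so a constant 250 mg gives the same readings.

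**Cycle 1 only.** One injection: 500/(14/7) = 250 mg/week, which reads 200%. Two injections: 1000/((14+14)/7) = 250 mg/week, again 200%. The ratio cannot tell them apart.

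**One missed injection, n of at least 2.** If the missed injection is neither the first nor the last cycle's, 500n/(4n) = 125 mg/week, which reads 100%. The true ratio is n/(n+1): 66.7% at 2 cycles, 83.3% at 5, 92.3% at 12. The first injection is excluded because missing it would move the first-dose date and so the duration; Protocol 6.1.1 starts dosing there in any case ("Patients will begin dosing assigned treatment on C1D1"). The last cycle's is excluded because missing it leaves open which cycle counts as last.

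**Size at a plausible treatment length.** SAP Section 5 says "The median PFS of Arm B is assumed to be 4.3 months". As a check on that input, 4.3/0.74 − 4.3 = 1.51 months, matching the stated improvement of about 1.5. Under Protocol 4.1, participants "will be treated until disease progression or other discontinuation criteria are met", so I use the median as a stand-in for time on treatment:

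- 4.3 × 30.4375 = 130.9 days; 130.9/28 = 4.67 cycles.
- Five cycles started: 120%.
- Stopped at the week-16 scan with the Cycle 5 injection withheld (four cycles): 125%. Scans in Protocol 1.3 are "every 8 weeks (±4 days) for the first 12 months and then every 12 weeks (±4 days) thereafter".
- With the 3.6-month assumption for the ESR1-mutation detected subset: 109.6 days, 3.91 cycles, four started: 125%.
- Over 3 to 8 months: 91.3 days, four started, 125%; 243.5 days, nine started, 10/9 = 111.1%.

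**The case against.** The strongest reply is that little rests on this ratio. SAP 4.7.1 also summarises cycles received, omissions, reductions and delays, so a missed injection is visible elsewhere, and all of it is reported as deemed appropriate. Protocol 9.4.2.5 lists dose intensity but not relative dose intensity. That stands, and it keeps the point minor. It does not make the formula right.

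The anchor is also loose. The 4.3 months is PFS from randomization for fulvestrant and exemestane together. Protocol 7.1 allows stopping earlier for toxicity or by choice, and treatment past progression by exception. The documents give no fulvestrant share of Arm B. So 120% to 125% is conditional, and the number of patients affected is unknown.

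Three stronger readings are tempting but unsupported:

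- A reader might infer that most fulvestrant patients would read 120% or more. With exponential treatment time and stopping on any day, 1 − 0.5^(140/130.9) = 52% start five cycles or fewer. If stopping instead follows the 8-weekly scans with that day's injection withheld, progression after day 112 is found at week 24 (six cycles, 116.7%), and the share is 1 − 0.5^(112/130.9) = 45%. Neither timing is documented.
- A reader might attribute extreme values to the omitted injection. Death 7 days after the first injection reads 500/(7/7)/125 = 400%, but Day 15 was not yet due. That figure comes from ending the duration at death, a separate artefact.
- A reader might infer that the efficacy comparison is affected. No PFS or OS analysis uses this ratio.

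**Conclusion.** The concern holds as a minor error of definition. The (n+1)/n result follows from the SAP's own formulas and schedule and needs no outside assumption beyond on-schedule dosing and the standard duration rule. The 120% to 125% figure additionally assumes that fulvestrant treatment lasts about as long as the assumed Arm B median PFS.

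The effect is confined to a descriptive exposure summary for fulvestrant patients in Arm B. Exemestane uses the oral-drug formula and is unaffected. No alpha or sample-size result changes, and nothing here questions the dosing schedule itself.

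**What to change.** Keep relative dose intensity as an intensity and put the Day 15 injection into the planned dose:

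- **Last dose after Cycle 1:** planned intensity = planned dose per injection × (duration in weeks/4 + 1)/duration in weeks. On schedule this equals 500(n+1)/(4n) mg/week.
- **Last dose in Cycle 1:** planned cumulative dose is one injection for the 14-day duration and two for the 28-day duration, divided by that duration.
- **In the ratio,** use the same standard, untruncated duration for received and planned dose, so that death or loss to follow-up does not inflate it.
- Replace infusion with injection, since fulvestrant is given intramuscularly.

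Checks:

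- On-schedule dosing gives 100% at any n.
- Five cycles with one missed injection give 2500/3000 = 83%.
- Death 7 days after the first injection gives 500/500 = 100%.
- Protocol 6.1.1 permits "a delay for a maximum of 7 days of a cycle start not due to an AE". Five cycles with each later start 7 days late run (4 × 35 + 28)/7 = 24 weeks; planned dose is 500 × (24/4 + 1) = 3500 mg, and 3000/3500 = 86%. Delay still registers.

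A ratio of injections received to injections due, with due dates taken from recorded cycle starts, would read 100% in that last case. It would also need a date of the decision to stop, which neither document shows is recorded as data. The narrower change is therefore preferable.

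One limit remains: a patient with only the first injection reads 100% whether Day 15 was missed or not yet due, so the omissions summary still has to show that.

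The cost is one SAP definition and minor reprogramming. Reported fulvestrant figures will be lower than under the current formula.
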